6.6 Dose Modification (Escalation/Titration/Other)

6.6.1 Dose Modification due to Adverse Events

AEs (both nonserious and serious) associated with MK-1454 and/or pembrolizumab exposure may represent an immunologic etiology. These AEs may occur shortly after the first dose or several months after the last dose of treatment.

The CTCAE Version 5.0 must be used to grade the severity of AEs. The investigator may attribute each toxicity event to MK-1454 alone, to pembrolizumab alone, or to the combination, and modify the dose according to [Table 5](#), [Table 6](#), and [Table 7](#). If a dose modification for toxicity occurs with MK-1454, the dose may not be re-escalated to the dose that preceded the dose modification. If 1 (or more) treatment is held for toxicity, the schedule for restarting the agents should correspond with the next treatment cycle once the toxicity is resolved.

Holding of 1 treatment and not the other treatment is appropriate if, in the opinion of the investigator, the toxicity is clearly related to one of the study interventions. For example, in the combination arm (Arm 1), if MK-1454 is held due to an AE attributed to it, then pembrolizumab may continue to be administered. Appropriate documentation is required with regard to which treatment the investigator is attributing the AE. If, in the opinion of the investigator, the toxicity is related to the combination of 2 treatments, then both treatments should be held according to recommended dose modifications.

Participants may have only 1 dose modification of MK-1454 throughout the course of the study. If further toxicity occurs or the criteria for resuming treatment are not met, the participant must be discontinued from MK-1454. If a participant experiences several toxicities and there are conflicting recommendations, follow the most conservative recommendation.

Exceptional circumstances to following the dose modification tables below may be considered after consultation with the Sponsor.

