6.6.1.1 Dose Modification for MK-1454

Guidelines for dose modification and/or treatment discontinuation for drug-related injection site reactions and for CRS AEs are provided in [Table 5](#) and [Table 6](#), respectively.

The investigator should first assess an AE to determine the CTCAE Version 5.0 severity grade. For AEs that are \leq Grade 2, the decision to hold treatment is per medical assessment by the investigator. Once the AE has resolved to Grade 0 or 1, treatment with MK-1454 can be restarted. If the AE persists, discuss with the Sponsor with regard to selecting a different injection site or discontinuation. MK-1454 should be discontinued permanently following a severe or life-threatening AE.

In case toxicity does not resolve to Grade 0-1 within 12 weeks after last intervention, MK-1454 should be discontinued after consultation with the Sponsor.

With investigator and Sponsor agreement, participants with a laboratory AE still at Grade 2 after 12 weeks may continue intervention in the study only if asymptomatic and controlled.

After any Grade 4 drug-related AE, participants should not restart study intervention without consultation with the Sponsor (Toxicity must have resolved to Grade 0-1 or baseline prior to restarting).

Pembrolizumab treatment will be modified for the AEs described in Section 6.6.1.4.

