6.6.1.1.1 Guidelines for Management of Intratumoral Injection Site Reactions

Guidelines for management of injection site reaction from intratumoral injection of MK-1454 are detailed in [Table 5](#).

Table 5 Intratumoral Injection Site Reaction Management Guidelines

NCI CTCAE Grade	MK-1454 Dose Modification	Treatment
Grade 1 Tenderness with or without associated symptoms (eg, warmth, erythema, itching)	No dose reduction warranted.	Observe. Dose to be held per medical assessment of the investigator. Analgesia as needed.
Grade 2 Pain; lipodystrophy; edema; phlebitis	Per medical assessment of the investigator: 
 Consider holding dose until resolution to Grade 1 or baseline. Consider decreasing dose of IT MK-1454 to [REDACTED] and limit injections to a maximum of 2 lesions per study visit. If AE persists, discuss continuation with Sponsor. 	Observe. Local care to injection site. Analgesia as needed. Consider injection into a different lesion, if available.
Grade 3 Ulceration or necrosis; severe tissue damage; operative intervention indicated	
 Hold dose until resolution to Grade 1 or Baseline. Decrease dose of IT MK-1454 to [REDACTED] and limit injections to a maximum of 2 lesions per study visit. If AE persists, discuss continuation with Sponsor. 	Wound care with consultation from institutional wound care specialist. Analgesia as needed. Consider injection into a different lesion, if available.
Grade 4 Life-threatening consequences; urgent intervention indicated	
 Permanently discontinue IT MK-1454 treatment. 	Aggressive wound care with surgical consultation. Analgesia as needed.

AE adverse events; CTCAE Common Terminology Criteria for Adverse Events (Version 5.0); IT intratumoral; NCI National Cancer Institute.

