
Grade 3
 
Prolonged (eg, not rapidly responsive to symptomatic medication); recurrence of symptoms following initial improvement; hospitalization indicated for clinical sequelae (eg, renal impairment, pulmonary infiltrates).
	
 • Hold dose until resolution to Grade 1 or baseline. • Decrease dose of IT MK-1454 to [redacted] and limit injections to a maximum of 2 lesions per study visit. • If AE persists, discuss continuation with Sponsor. 	
Additional appropriate medical therapy may include, but is not limited to:
 
 IV fluids NSAIDS Acetaminophen Narcotics Oxygen Vasopressors Corticosteroids Anti-IL6 (eg, tocilizumab) Empiric antibiotics 
Participants with \geq Grade 3 CRS need to be monitored very closely, likely in an intensive care setting.
	
For Grade 3 CRS, discuss with Sponsor prior to restart of study intervention. Upon approval by Sponsor, MK-1454 may be restarted at [redacted] after AE resolves back to baseline or to Grade 1.
 
Participant may be premedicated 1.5 hours(\pm 30 minutes) prior to study intervention administration with acetaminophen 500 to 1000 mg po (or equivalent dose of antipyretic).

Grade 4
 
Life-threatening consequences; pressor or ventilatory support indicated.
	
 • Permanently discontinue IT MK 1454 treatment. 	
Additional appropriate medical therapy may include, but is not limited to:
 
 IV fluids NSAIDs Acetaminophen Narcotics Oxygen Vasopressors Corticosteroids Anti-IL6 (eg, tocilizumab) Empiric antibiotics 
Participants with \geq Grade 3 CRS need to be monitored very closely, likely in an intensive care setting.
	
Permanently discontinue study intervention in participants who develop Grade 4 CRS.

AE adverse events; CRS cytokine release syndrome; CTCAE Common Terminology Criteria for Adverse Events (Version 5.0); IT intratumoral; IV intravenous; NCI National Cancer Institute; NSAID nonsteroidal anti inflammatory drug; po orally.

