7 DISCONTINUATION OF STUDY INTERVENTION AND PARTICIPANT WITHDRAWAL

7.1 Discontinuation of Study Intervention

Discontinuation of study intervention does not represent withdrawal from the study.

As certain data on clinical events beyond study intervention discontinuation may be important to the study, they must be collected through the participant's last scheduled follow-up, even if the participant has discontinued study intervention. Therefore, all participants who discontinue study intervention prior to completion of the protocol-specified treatment period will still continue to participate in the study as specified in Section 1.3 and Section 8.1.9, or if available, Protocol Clarification Letter.

Participants may discontinue study intervention at any time for any reason or be discontinued from the study intervention at the discretion of the investigator should any untoward effect occur. In addition, a participant may be discontinued from study intervention by the investigator or the Sponsor if study intervention is inappropriate, the study plan is violated, or for administrative and/or other safety reasons. Specific details regarding procedures to be performed at study intervention discontinuation are provided in Section 8.1.9.

A participant must be discontinued from study intervention but continue to be monitored in the study for any of the following reasons:

- The participant or participant's legally acceptable representative requests to discontinue study intervention.
- The participant interrupts study intervention administration for more than 12 consecutive weeks.
- The participant has a medical condition or personal circumstance which, in the opinion of the investigator and/or Sponsor, placed the participant at unnecessary risk from continued administration of study intervention.
- The participant has a confirmed positive serum pregnancy test.
- Confirmed radiographic disease progression outlined in Section 8.2 (exception if the Sponsor approves treatment continuation).
- Progression or recurrence of any malignancy, or any occurrence of another malignancy that requires active treatment.
- Any study-intervention-related toxicity specified as a reason for permanent discontinuation in the guidelines for dose modification due to AEs in Section 6.6.
- Intercurrent illness other than another malignancy, as noted above, that prevents further administration of treatment.
- Investigator's decision to discontinue treatment.

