10.3.4 Recording AE and SAE

AE and SAE recording

- When an AE/SAE occurs, it is the responsibility of the investigator to review all documentation (eg, hospital progress notes, laboratory, and diagnostics reports) related to the event.
- The investigator will record all relevant AE/SAE information on the AE eCRFs/worksheets at each examination.
- It is not acceptable for the investigator to send photocopies of the participant's medical records to the Sponsor in lieu of completion of the AE eCRF page.

- There may be instances when copies of medical records for certain cases are requested by the Sponsor. In this case, all participant identifiers, with the exception of the participant number, will be blinded on the copies of the medical records before submission to the Sponsor.
- The investigator will attempt to establish a diagnosis of the event based on signs, symptoms, and/or other clinical information. In such cases, the diagnosis (not the individual signs/symptoms) will be documented as the AE/SAE.

Assessment of intensity/toxicity

- An event is defined as “serious” when it meets at least 1 of the predefined outcomes as described in the definition of an SAE, not when it is rated as severe.

The investigator will make an assessment of intensity for each AE and SAE (and other reportable safety event) according to the NCI CTCAE, Version 5.0. Any AE that changes CTCAE grade over the course of a given episode will have each change of grade recorded on the AE eCRFs/worksheets.

Grade 1: Mild; asymptomatic or mild symptoms; clinical or diagnostic observations only; intervention not indicated.

Grade 2: Moderate; minimal, local or noninvasive intervention indicated; limiting age-appropriate instrumental ADL.

Grade 3: Severe or medically significant but not immediately life-threatening; hospitalization or prolongation of hospitalization indicated; disabling; limiting self-care ADL.

Grade 4: Life-threatening consequences; urgent intervention indicated.

Grade 5: Death related to AE.

Assessment of causality

- Did the Sponsor’s product cause the AE?

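### The permanent-stop sentence for MK-1454 in Section 6.6.1.1 has no exception for Tables 5 and 6, which allow a reduced-dose restart after a Grade 3 injection site reaction or CRS

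*Combined protocol and SAP*

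**What the plan says.** Section 6.6.1.1 opens by assigning injection site reactions and CRS to Tables 5 and 6. It tells the investigator to grade the event by CTCAE version 5.0 and leaves holding at Grade 2 or below to the investigator's judgment. It then states: "MK-1454 should be discontinued permanently following a severe or life-threatening AE". No exception follows.

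Section 10.3.4 gives the severity scale: "Grade 3: Severe or medically significant but not immediately life-threatening". Grade 4 is the life-threatening category.

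Table 5 describes a Grade 3 injection site reaction as "Ulceration or necrosis; severe tissue damage; operative intervention indicated". Its first instruction is "Hold dose until resolution to Grade 1 or Baseline". The dose is then lowered, with at most 2 lesions injected per visit, and the sponsor is to be consulted if the event persists.

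Table 6 gives the same hold and reduction for Grade 3 CRS and requires a discussion with the sponsor before restart: "Upon approval by Sponsor, MK-1454 may be restarted at" a level that is blacked out in the public copy. Both tables reserve the permanent stop for Grade 4.

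Section 6.6.1 tells investigators to modify the dose by Tables 5, 6 and 7, and allows departures from the tables only in exceptional cases after talking to the sponsor.

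**The concern.** The text and the tables give opposite instructions for the same Grade 3 event: end MK-1454 for good, or resume it at a lower dose. No participant can be managed under both. The events are serious ones: ulceration, necrosis or a reaction needing surgery, and CRS needing hospital care. The drug is investigational and is injected weekly for the first six weeks. At stake is whether Arm 1 participants who have had such a reaction are re-exposed on a consistent basis across sites. Whichever course a site takes, a monitor could cite the other instruction as a deviation.

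**Working it through.** No arithmetic applies. The check sets the MK-1454 rules side by side by grade.

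| CTCAE grade | Section 6.6.1.1 text | Table 5, injection site reaction | Table 6, CRS |
|---|---|---|---|
| 2 or below | Holding is at the investigator's judgment; restart at Grade 0 or 1 | Grade 1: no reduction. Grade 2: consider a hold and a reduction | Same as Table 5 |
| 3 | Stop permanently | Hold, then lower dose, at most 2 lesions; sponsor contact only if the event persists | Hold, then lower dose, at most 2 lesions; restart needs sponsor approval |
| 4 | Stop permanently | Stop permanently | Stop permanently |

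The rules agree at Grade 4 and are compatible at Grade 2 and below. They conflict at Grade 3.

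1. **Does *severe* mean Grade 3?** Section 10.3.4 attaches the word to Grade 3, with *medically significant* as an alternative, and attaches *life-threatening* to Grade 4. The paragraph in 6.6.1.1 starts from the CTCAE grade and deals with Grade 2 and below separately, so the stop sentence naturally covers Grades 3 and 4. Table 5 also uses the word in its Grade 3 row. The Grade 3 CRS row does not, so for CRS the reading rests on Section 10.3.4.

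2. **Does the stop sentence exclude injection site reactions and CRS?** Not in words. It comes after the line that introduces the two tables. The sentence just before it suggests choosing another injection site if the event persists, so injection site events are within the paragraph's scope.

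3. **Does the tie-break rule resolve it?** Section 6.6.1 says: "If a participant experiences several toxicities and there are conflicting recommendations, follow the most conservative recommendation". That covers one participant with more than one toxicity, not two rules for a single event. If it did apply here, the Grade 3 resumption rows could never operate.

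4. **Can a site act alone?** For Grade 3 CRS, no: restart needs sponsor approval. For a Grade 3 injection site reaction that resolves, yes: Table 5 lets the site lower the dose and re-inject without contacting the sponsor.

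5. **Cross-reference.** Section 6.6.1.1 ends by sending the reader to Section 6.6.1.4 for pembrolizumab modifications. The protocol has no such section; the content is in 6.6.1.2.

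**The case against.** The strongest reply is that the tables plainly govern. Section 6.6.1 directs dose changes to them and treats departures as exceptional, Section 6.6.1.1 opens by assigning these two reactions to them, and a specific rule normally displaces a general one. Re-exposure is also limited: a participant may have only one MK-1454 dose modification, and further toxicity ends the drug. Most of this stands, and it is why the tables are probably the intended rule. It does not supply the missing exception, and a reader who starts from the stop sentence finds nothing that limits it.

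A reader might go further in three ways that the documents do not support.

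- **That Section 7.1 makes the stop mandatory.** It lists as a reason to discontinue "Any study-intervention-related toxicity specified as a reason for permanent discontinuation in the guidelines for dose modification due to AEs in Section 6.6". Section 6.6.1.1 uses the phrase about dose modification guidelines for Tables 5 and 6, which name a permanent stop only at Grade 4. Section 7.1 therefore supports the tables at least as well as the stop.
- **That the stop sentence disregards causality.** It has no attribution wording of its own, but Section 6.5.3 describes Section 6.6 as guidance for drug-related events, and Section 6.6.1 says: "The investigator may attribute each toxicity event to MK-1454 alone, to pembrolizumab alone, or to the combination". Context covers this.
- **That the Grade 4 sentence in 6.6.1.1 is a second contradiction.** It bars restart of study intervention without sponsor consultation and does not name the drug. A site can obey it together with a permanent MK-1454 stop.

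**Conclusion.** The inconsistency is real and is not produced by redaction. At Grade 3, Section 6.6.1.1 and Tables 5 and 6 give incompatible instructions for injection site reactions and CRS, and no stated exception settles which applies. The clearest practical gap is the Grade 3 injection site reaction, where two sites can take opposite courses without sponsor contact. For CRS, the approval step keeps the sponsor in the decision. The conclusion rests on reading *severe* as Grade 3, as Section 10.3.4 does.

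The affected group is Arm 1, about 100 of about 200 participants; how many would have such an event is unknown because the Phase 1 toxicity detail is blacked out. A reader might infer that the secondary endpoint of discontinuation due to an AE is materially distorted. The documents do not support a figure. One would need a Grade 3 event rate, the share of sites following each rule, and a statement that stopping MK-1454 alone counts as discontinuing study intervention. The last is unclear, because pembrolizumab may continue while MK-1454 is held. Some effect on that rate is possible, but the between-arm safety intervals are descriptive under Section 9.6.2. The primary response rate test, its alpha and its power are untouched.

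**What to change.** Open the stop sentence in Section 6.6.1.1 with an exception stating that injection site reactions and CRS are managed according to Tables 5 and 6. Add the grade numbers, Grade 3 after *severe* and Grade 4 after *life-threatening*, so that the sentence and the CTCAE scale match. Correct the cross-reference from Section 6.6.1.4 to 6.6.1.2.

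If the sponsor in fact wants a permanent stop at Grade 3, leave the sentence without the exception and remove the reduced-dose resumption from the Grade 3 rows of Tables 5 and 6.

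The change should stay this narrow. New attribution rules for every Grade 3 and Grade 4 event could collide with Table 7, which continues treatment through Grade 2 to 4 hypothyroidism and, under footnote d, lets some Grade 4 endocrine events resume. Assigning the Grade 4 restart sentence to pembrolizumab would also add a rule that the text does not contain.

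The cost is one clause, two grade labels and one cross-reference in a routine amendment, with a note to sites. Design, sample size and analysis do not change.

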6.6.1.1.1 Guidelines for Management of Intratumoral Injection Site Reactions

Guidelines for management of injection site reaction from intratumoral injection of MK-1454 are detailed in [Table 5](#).

Table 5 Intratumoral Injection Site Reaction Management Guidelines

NCI CTCAE Grade	MK-1454 Dose Modification	Treatment
Grade 1 Tenderness with or without associated symptoms (eg, warmth, erythema, itching)	No dose reduction warranted.	Observe. Dose to be held per medical assessment of the investigator. Analgesia as needed.
Grade 2 Pain; lipodystrophy; edema; phlebitis	Per medical assessment of the investigator: 
 Consider holding dose until resolution to Grade 1 or baseline. Consider decreasing dose of IT MK-1454 to [REDACTED] and limit injections to a maximum of 2 lesions per study visit. If AE persists, discuss continuation with Sponsor. 	Observe. Local care to injection site. Analgesia as needed. Consider injection into a different lesion, if available.
Grade 3 Ulceration or necrosis; severe tissue damage; operative intervention indicated	
 Hold dose until resolution to Grade 1 or Baseline. Decrease dose of IT MK-1454 to [REDACTED] and limit injections to a maximum of 2 lesions per study visit. If AE persists, discuss continuation with Sponsor. 	Wound care with consultation from institutional wound care specialist. Analgesia as needed. Consider injection into a different lesion, if available.
Grade 4 Life-threatening consequences; urgent intervention indicated	
 Permanently discontinue IT MK-1454 treatment. 	Aggressive wound care with surgical consultation. Analgesia as needed.

AE adverse events; CTCAE Common Terminology Criteria for Adverse Events (Version 5.0); IT intratumoral; NCI National Cancer Institute.

6.6.1.1.2 Treatment for Cytokine Release Syndrome

CRS is defined in CTCAE Version 5.0 as a disorder characterized by nausea, headache, tachycardia, hypotension, rash, and shortness of breath. CRS occurs when lymphocytes (B cells, T cells, and/or natural killer cells) and/or myeloid cells (macrophages, dendritic cells, and monocytes) become activated and release inflammatory cytokines [Lee, D. W., et al 2014]. In addition to the symptomatology defined under CTCAE, CRS may present with fever, chills, myalgias, and malaise. Table 6 shows treatment guidelines for participants who experience CRS.

Table 6 Cytokine Release Syndrome Treatment Guidelines

NCI CTCAE Grade	MK-1454 Dose Modification	Treatment	Premedication at Subsequent Dosing

Grade 1
 
Mild reaction: Therapy interruption not indicated. Intervention not indicated.
	
No dose reduction warranted.
	
Increase monitoring of vital signs and oxygen saturation, as medically indicated, until the participant is deemed medically stable, in the opinion of the investigator.
	
None.

Grade 2
 
Therapy interruption indicated but responds promptly to symptomatic treatment (eg, NSAIDs, narcotics, IV fluids). Prophylactic medications indicated for ≤ 24 hours.
	
Per medical assessment of the investigator:
 
 • Consider holding dose until resolution to Grade 1 or baseline. • Consider decreasing dose of IT MK-1454 to CCI and limit injections to a maximum of 2 lesions per study visit. • If AE persists, discuss continuation with Sponsor. 	
Increase monitoring of vital signs and oxygen saturation, as medically indicated, until the participant is deemed medically stable, in the opinion of the investigator.
 
Additional appropriate medical therapy may include, but is not limited to:
 
 IV fluids NSAIDs Acetaminophen Narcotics Oxygen 
Perform fever workup to exclude infectious etiologies; treat neutropenia if present.
	
Participant may be premedicated with acetaminophen 1.5 hours (± 30 minutes) prior to study intervention administration 500 to 1000 mg po (or equivalent dose of antipyretic).

NCI CTCAE Grade	MK-1454 Dose Modification	Treatment	Premedication at Subsequent Dosing

Grade 3
 
Prolonged (eg, not rapidly responsive to symptomatic medication); recurrence of symptoms following initial improvement; hospitalization indicated for clinical sequelae (eg, renal impairment, pulmonary infiltrates).
	
 • Hold dose until resolution to Grade 1 or baseline. • Decrease dose of IT MK-1454 to [redacted] and limit injections to a maximum of 2 lesions per study visit. • If AE persists, discuss continuation with Sponsor. 	
Additional appropriate medical therapy may include, but is not limited to:
 
 IV fluids NSAIDS Acetaminophen Narcotics Oxygen Vasopressors Corticosteroids Anti-IL6 (eg, tocilizumab) Empiric antibiotics 
Participants with \geq Grade 3 CRS need to be monitored very closely, likely in an intensive care setting.
	
For Grade 3 CRS, discuss with Sponsor prior to restart of study intervention. Upon approval by Sponsor, MK-1454 may be restarted at [redacted] after AE resolves back to baseline or to Grade 1.
 
Participant may be premedicated 1.5 hours(\pm 30 minutes) prior to study intervention administration with acetaminophen 500 to 1000 mg po (or equivalent dose of antipyretic).

Grade 4
 
Life-threatening consequences; pressor or ventilatory support indicated.
	
 • Permanently discontinue IT MK 1454 treatment. 	
Additional appropriate medical therapy may include, but is not limited to:
 
 IV fluids NSAIDs Acetaminophen Narcotics Oxygen Vasopressors Corticosteroids Anti-IL6 (eg, tocilizumab) Empiric antibiotics 
Participants with \geq Grade 3 CRS need to be monitored very closely, likely in an intensive care setting.
	
Permanently discontinue study intervention in participants who develop Grade 4 CRS.

AE adverse events; CRS cytokine release syndrome; CTCAE Common Terminology Criteria for Adverse Events (Version 5.0); IT intratumoral; IV intravenous; NCI National Cancer Institute; NSAID nonsteroidal anti inflammatory drug; po orally.

